6.4.2. Extension Study (approximately 2 years of age up to the 6th birthday)

 Table 8 presents the list of procedures for the extension study.

Note that although extension study enrolment ideally occurs at the time of the subjects' second birthdays, enrolment into, and first contact for, the extension study may take place at any time between the end of the primary study and the subject's 6th birthday.

After the first extension study contact, subjects will be contacted around the time of each subject's birthday and (approximately) quarterly during the intervals between (a) first contact and next birthday; (b) subsequent birthdays.

Site staff may contact subjects more frequently than indicated in Table 8 if *consistent with the language of the local ICF* and considered necessary by the study physician. Parents will be encouraged to seek a clinical assessment of their child in between quarterly contacts and/or during quarterly contacts whenever their child develops wheezing and/or breathing difficulties.

Refer to Section 6.6 and the SPM for additional details.

200150 (EPI-RSV-005 BOD)

Protocol Amendment 3 Final

Table 8List of extension study procedures (from the age of approximately 2 years up to the 6th birthday) (Amended 15-
DEC-2017)

Epoch 2	Data collection				
Visit/Contact	First Contact a	Quarterly Contact ^{b, c}	Annual contact ^{, c, d}		
Time points	Extension study enrolment		Around the 2 ^d , 3 rd , 4 th , 5 th , and 6 th birthdays (+ 3 months)		
Perform / document results of these procedures					
Informed consent for extension	•				
Check inclusion/exclusion criteria for extension	•				
Collect demographic data for extension	•				
Collect data on potential symptoms and risk factors for wheeze and asthma	•	• (applies to Version 1.0 of the quarterly contact script)	• d		
Record episodes of wheeze, asthma, and troublesome lungs	•	•	● d		
Collect data about medication used to treat asthma, wheeze, or troublesome lung symptoms	•	•	● d		
Review / assess information about asthma diagnoses and medication use based on medical record abstraction and subject information over approximately the past 12 months or longer	• e		• e		
Interim analysis after 4th birthday; Final analysis after 6th birthday			•		
Investigator sign-off on eCRF before analysis			● f		
Study conclusion for extension			• g		
and enter data into these eCRF modules					
	 First Contact Annual ^a 	• Quarterly	QuarterlyAnnual		

• indicates a study procedure that requires documentation in the individual eCRF.

^a At the time of first contact, if delayed, all missed annual assessments of asthma will be completed retrospectively by the Investigator.

^b At approximately 3, 6 and 9 months (+/- 1.5 months), between consecutive birthdays. There should be at least one month between each Quarterly Contact ^c Both Quarterly parent/LAR interview AND Annual investigator review/assessment data to be collected and reported.

200150 (EPI-RSV-005 BOD)

Protocol Amendment 3 Final

^d To accurately complete investigator-targeted asthma questions, up-to-date information about all asthma, wheeze, and troublesome lung episodes as well as a review of any and all potential asthma medications that were taken by the subject will be needed for the accurate completion of the investigator assessment. Refer to Section 6.6.4.2.

• The investigator will supplement information from parents with review of routine medical records/ consultation with routine health care provider(s), as appropriate.

^f After completion of 4th birthday annual contact (for interim analysis), and at study conclusion

^g Study conclusion for the extension will be at the last contact, at child's 6th birthday.

6.5. Detailed description of study procedures for the Primary Study period (from birth up to 2 years of age)

6.5.1. Informed consent

The signed/witnessed/thumb printed informed consent of the subject's parent(s)/LAR(s) must be obtained before study participation. Refer to Section 6.1 for the requirements on how to obtain informed consent.

- In case of anticipated twins (or *other multiple births*), an ICF needs to be signed for each expected child before the start of delivery.
- In case of unexpected twins (or *other multiple births*), only the children for whom an ICF has been signed before birth can be enrolled. This should occur as per the birth order.

6.5.2. Check inclusion and exclusion criteria applicable before birth

Check all applicable inclusion and exclusion criteria applicable before birth as described in Sections 5.3.1 and 5.4.1 before enrollment. A pre-selected child who does not meet the eligibility criteria should be considered a screening failure.

6.5.3. Subject number allocation and registration in SBIR-Screening

Subject numbers will be assigned sequentially to subjects whose parent(s)/LAR(s) have consented for their child participation in the study, according to the range of subject numbers allocated to each study center.

• In case of anticipated twins (or *other multiple births*), a subject number will be assigned sequentially to each child for whom the consent has been obtained, as per the birth order, where the first born will be associated with the lowest subject number, the second born with the successive subject number, etc.

After obtaining the ICF and confirming eligibility, the subject needs to be entered in to the SBIR screening module. SBIR will control the recruitment rate as per an allocated target.

6.5.4. Collection of expected birth date

Record the expected delivery date as required in the subject's eCRF.

6.5.5. Collection of cord blood sample

Refer to the Module on Biospecimen Management in the SPM for general handling of blood samples.

A volume of up to approximately 10 mL of whole cord blood sample will be collected from all subjects at birth, which should yield up to approximately 3 mL of serum. In case

less than 3 mL of whole blood is collected, the subject will be considered a screening failure and the sample collected needs to be discarded according to local procedure.

Details of the sample collection such as duration of processing steps and storage conditions need to be collected and recorded in the eCRF in order to allow adjustment for these variables in the primary analyses and to explore the impact of collection variables on the measured antibody titer.

Cord blood samples collected will provide RSV- antibody levels in the child, at birth.

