9.7.3. Tertiary Objectives

• To explore the association of co-infections with the incidence of RSV-associated LRTI and/or severe LRTI (as determined by the LRTI case definition and severity scale) using xTAGTM RVP Fast assay.

For each of the other respiratory viruses, incidence rates will be calculated as the number of RSV-associated LRTI/severe LRTI cases associated co-infected with the virus over the number of children-years observations.

• To explore the association of RSV and other respiratory viruses with the incidence of LRTI and/or severe LRTI (as determined by the LRTI case definition and severity scale) using xTAGTM RVP Fast assay.

For each of the respiratory viruses, incidence rates will be calculated as the number of LRTI/severe LRTI cases associated with the virus over the number of children-years observations.

• To explore the association of RSV viral load with the incidence of RSVassociated RTI, LRTI and/or severe LRTI (as determined by the LRTI case definition and severity scale).

Descriptive analyses (mean, median, min, max) of viral load assessed by the RSV RTqPCR of RSV RTI, RSV LRTI and severe LRTI cases will be tabulated.

• To explore the impact of changes to the symptoms and threshold levels of symptoms in the LRTI case definition and severity scale.

Frequency tables will summarize the proportion of RSV-associated LRTI/ severe LRTI cases associated with a list of symptoms and clinical parameters, overall and by age categories.

This will help us to determine potential areas of improvement of the LRTI case definition and severity scale. Incidence rates of RSV-associated LRTI/severe LRTI will be calculated for any proposal of modification of the LRTI case definition and severity scale.

• To explore the impact of variations in cord-blood sample collection variables on the stability of test results.

The measured maternal antibody levels will be assessed versus variability in sample collection variables. This involves assessment versus various continuous and categorical variables and an overall comparison between samples as classified 'according to recommended procedure' and 'not according to recommended procedure'.

The measured maternal antibody levels by duration of the processing step and overall process duration will be analysed graphically and by log-linear regression.

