6.9. Neutralizing antibodies over time and protection against RSV disease analysis

6.9.1. Analysis of secondary objective: Association between RSV disease and cord blood neutralizing antibodies

The analysis will be based on PPS and will be done considering the 2 age intervals:

- 0-2 months
- 0-5 months

The analysis will be realized only on the first episode (and not recurrent events) occurring during the considered age interval using a stepwise approach.

Step 1: Descriptive analysis:

Descriptive analyses (seropositivity rate with 95% CIs, geometric mean, median, min, max) of RSV neutralizing antibodies in the baseline cord blood samples will be presented by WHO RSV LRTI and WHO RSV severe LRTI case status; and with overlapping and non-overlapping disease severity.

In addition, descriptive analyses (seropositivity rate with 95% CIs, geometric mean, median, min, max) of RSV neutralizing antibodies in the baseline cord blood samples will be analysed according to the following endpoints:

- All RSV positive nasal swab samples (see details 6.1.2)
 - WHO RSV LRTI
 - WHO RSV LRTI (excluding WHO RSV severe LRTI)
 - WHO RSV severe LRTI
- Descriptive analyses (mean, median, min, max) of the total viral load of RSV according to the quartiles of neutralizing antibodies detected in the cord blood will be described.

Step 2: Cox models:

The impact of the level of RSV neutralizing antibodies in the baseline cord blood samples on the incidence of first event of WHO RSV-LRTI and WHO RSV-severe LRTI separately will be assessed through Cox models.

Univariate and multivariable Cox models will be presented. The following covariates may be considered in the multivariable model

- General:
 - Country of birth
 - Gender
 - Time of birth relative to the transmission season
- Characteristics at birth:
 - Gestational age at birth
 - Birth weight
 - Apgar at 5 mins of age
 - Caesarian section
- Family history:
 - First degree relative with family history of asthma

Statistical Analysis Plan Amendment 1 Final

- Living environment and household composition:
 - Highest education level of the mother
 - Highest education level of the father
 - Number of people living in the household at month 3
 - Number of other children (<18 years old) living in the household at month 3
 - Subject in regular close contact with toddlers at month 3
 - The child live in a surrounding where people smoke daily at month 3
 - Breast feeding *

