* Time dependent covariate; status is yes of subject ever breastfed from DOB until the end of breastfeeding given in the surveillance visit. Last day of month will be imputed for any partial date of breastfeeding end date.

Covariates with univariate p-value less than 0.1 will be included in the multivariable model. The number of covariates included in the model will depend on the number of events (at least 10 events per covariates).

Please note that the multivariable model will be performed only if the number of events is sufficient (at least 10 events per covariates). In addition, depending on the data other models could be explored or the model could be simplified.

Step 2-a: RSV neutralizing antibodies classified as a binary variable: Seropositive and seronegative:

In a first step, the RSV neutralizing antibodies in the baseline cord blood samples will be introduced in the model as binary variable. If the effect of RSV neutralizing antibodies as binary variable is significant we process to the next step.

Step 2-b: RSV neutralizing antibodies classified as semi-quantitative variable: Ouartiles

In a second step, the RSV neutralizing antibodies levels will be introduce in the model using quartiles. And the Cox models will be performed as describe in the previous paragraph (RSV neutralizing antibodies as quantitative variable – Step 2-a). If the effect of neutralizing antibodies as semi quantitative variable is significant, we proceed to next step.

Step 2-c: RSV neutralizing antibodies classified as continuous variable:

In a third step, the RSV neutralizing antibodies levels might be treated as continuous variable in Cox models to evaluate how each unit of neutralizing antibody level change impacts on the above clinical outcomes. The Cox models will be performed as describe in the previous section (with log of RSV neutralizing antibodies as quantitative variable). For the subjects with antibody level below the LLOQ, a value of LLOD/2 will be imputed.

Note that depending on the results, a quantitative association between RSV-associated LRTI, RSV-associated severe LRTI and RSV neutralizing antibodies in the baseline cord blood samples could be further explored and described more in details in a separate Additional Analysis Request.

6.9.2. Analysis of secondary objective: prevalence of RSV infection at 2, 4, 6, 12, 18 and 24 months

The analysis will be based on PPS sub-cohort for this objective.

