6.9.3. Analysis of tertiary objective: natural decay of maternal neutralizing antibodies

The analysis will be based on total sub-cohort subject with blood sampling at month 2, 4, 6, and 12 for this objective.

The decay of maternal antibody levels over time will be analysed graphically and by a linear regression of the log of maternal antibody levels. A true, natural decay curve will be explored by stochastically reducing the sample to uninfected subjects only. The following steps will be taken to identify, confirmed and suspected infected subjects to eliminate these from the sample;

STEP 1: Subjects with an RSV positive *nasal swab* during the study before time of sampling will be eliminated. Note that such subjects are removed from the analysis because they are infected by RSV; as a consequence their antibody levels are no longer maternal antibody levels.

STEP 2: Run the model and compute expected value based on the decay curve for each subjects

200150 (EPI-RSV-005 BOD)

Statistical Analysis Plan Amendment 1 Final

STEP 3: Subjects with an antibody titer at the sampling time that is more than 2-fold above the expected value based on their baseline (cord blood) value and the established decay curve will be considered to have been infected, eliminated and the decay curve refined.

STEP 4: Step 3 is repeated up to 5 times until the most accurate decay curve is established.

The natural decay of antibody will be determined using linear regression between the log of antibody level (Y) and time t (age in months) with subject as a random effect. Indeed, all subjects have RSV neutralizing antibodies measured at birth (cord blood). And, each subject of the Total sub-cohort will be randomly selected to be sampled for RSV neutralizing antibodies at one of the following time points: 2, 4, 6, and 12 months. For the natural decay model, subjects will have maximum 2 RSV neutralizing antibodies measures, one at birth and one either at 2 months or 4 or 6 or 12 months.

A table will describe the decay rate and half-life statistics of the natural decay model.

A descriptive table will describe the serology status (positive/negative) according to the natural decay analysis.

A sensitivity analysis of the decay curve will be explored in sub-sample consisting of the subjects born 'off-season' as these have the lowest likelihood of having been infected.

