Please note that additional exploratory analysis could be perform depending on the data and that the decay analysis could be adapted depending on the number of samples < LLOQ for each time points, especially for the later time points. Specific analysis of the twins could be explored if the number of twins reaches at least 50 subjects. Additional models such as models including a t^2 term or some covariates could be explored.

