6.11. Evaluation of cord blood collection variables, disease surveillance and protocol procedures

6.11.1. Analysis of tertiary objective: cord blood collection, storage and processing

The objective is to assess the effect of cord blood collection, and storage and processing on the neutralizing antibody level in the cord blood.

Number and percentage of subjects follow each cord-blood collection, storage, and processing categories will be calculated. Descriptive statistics of geometric mean, standard deviation, median, and range will be calculated for neutralizing antibody level in the cord blood for each of the collection, storage, and processing category.

The duration between collection and completion of processing will be calculated. Scatter plots will be used to assess the association between the duration of processing and cord blood antibody levels.

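### Cord-blood handling is recorded to allow adjustment, but no prespecified SAP antibody analysis uses it and SAP section 9 does not say so; a sensitivity analysis would cover the gap cheaply

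*Protocol*

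**What the plan says.** Protocol 6.5.5 gives two purposes for recording handling details: "in order to allow adjustment for these variables in the primary analyses and to explore the impact of collection variables" on the titre. Protocol section 9 does not turn the first purpose into a model term. It plans only the tertiary handling analysis (9.7.3), in which "The measured maternal antibody levels by duration of the processing step and overall process duration will be analysed graphically and by log-linear regression", with group means and t-tests for storage condition and tube type.

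The SAP uses the cord titre in three places.

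- **Cox models (6.9.1).** "The impact of the level of RSV neutralizing antibodies in the baseline cord blood samples on the incidence of first event of WHO RSV-LRTI" is estimated with the titre as a binary, quartile and then continuous variable; WHO RSV-severe LRTI is treated the same way. The list headed "The following covariates may be considered in the multivariable model" covers country, gender, birth season, birth characteristics, family asthma, household variables and breast feeding. It has no storage, tube or processing-time variable. Nor do Table 15 or Templates 43-45.
- **Decay model (6.9.3).** "The natural decay of antibody will be determined using linear regression between the log of antibody level (Y) and time t (age in months"). The model's only other term is a subject-level random effect.
- **Infection status (6.9.2).** At months 2, 4, 6 and 12 a child counts as infected if the titre is at least 2-fold above the value expected from that child's own cord titre and the modelled decay. Months 18 and 24 use a fixed assay cut-off.

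The SAP's handling analysis (6.11.1) consists of counts, descriptive titres by category, and plots: "Scatter plots will be used to assess the association between the duration of processing and cord blood antibody levels". Section 9 declares that the comparison of recommended with non-recommended procedure is replaced by descriptives. It says nothing about adjustment.

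**The concern.** The cord titre is the exposure in one secondary objective. It also anchors each child's expected titre in the prevalence objective (secondary) and the decay objective (tertiary). If some samples read low because of how they were stored or processed, the error enters all three. It adds noise to the exposure and so dilutes the hazard ratio. It lowers the starting point of the decay curve and so flattens it. It also lowers the expected titre of the affected children, so that an uninfected child passes the 2-fold line more easily.

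Neither adjustment nor exclusion guards against this. The elimination codes in SAP 5.2 cover consent, eligibility, randomisation to sampling, sampling schedule and missing results; none covers off-procedure cord samples. Template 56 allows for four storage conditions and four tube categories, by country. The plan therefore expects variation in handling, but sets no step for acting on what 6.11.1 finds.

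**Working it through.** The documents state no figure on this point, so there is none to reproduce. Loss sizes, titre SDs and half-lives are not given and are assumed below.

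**Children exposed to the infection rule.** From SAP Table 1, months 2, 4, 6 and 12 have 200 + 200 + 250 + 300 = 950 of 2000. Months 18 and 24 have 450 + 600 = 1050 and do not use the cord titre.

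**Hazard ratio.** Half the samples read low by a factor f, independently of true titre. On the log2 scale the added variance is v = 0.25 × (log2 f)², and the attenuation of the log hazard ratio is v/(SD² + v), where SD is that of the true titre.

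| Loss f | log2 f | v | SD 1 log2 | SD 1.5 log2 |
|---|---|---|---|---|
| 1.2 | 0.263 | 0.017 | 1.7% | 0.8% |
| 1.4 | 0.485 | 0.059 | 5.6% | 2.5% |
| 2 | 1.000 | 0.250 | 20% | 10% |

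**Decay rate.** I fitted a random-intercept slope to the 200/200/250/300 design, with within-subject correlation from 0 to 0.9. A 2-fold loss in every cord sample flattens the natural-log slope by 0.062-0.077 per month. The effect is linear in the mean log loss, so with half the samples affected it is 0.031-0.038, and a true half-life of 2 months reads 2.20-2.25. A 1.2-fold loss in half the samples gives 2.05-2.06.

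**Infection rule, affected child only.** With the curve held fixed, the share of uninfected children called infected is 1 − Φ((1 − log2 f)/SD), where SD is that of observed minus expected titre. With no loss it is 15.9% (SD 1 log2) or 2.3% (SD 0.5). For f = 1.2, 1.4 and 2 it is 23.1%, 30.3% and 50% (SD 1), or 7.0%, 15.2% and 50% (SD 0.5).

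**Infection rule, whole group.** Half the samples are affected and the slope is refitted through the cord value. The slope shift is b = (Σt/Σt²) × (log2 f)/2 = (6300/56200) × (log2 f)/2 = 0.112 × (log2 f)/2 per month. The threshold at month t becomes 1 + bt for unaffected children and 1 + bt − log2 f for affected children. Averaged over the 950:

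| Loss f | SD 1 log2 (no loss: 15.9%) | SD 0.5 log2 (no loss: 2.3%) |
|---|---|---|
| 1.2 | 16.9% | 3.2% |
| 1.4 | 18.2% | 4.9% |
| 2 | 22.4% | 12.7% |

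The flatter curve protects the unaffected children and partly offsets the excess among the affected ones. These figures leave out the repeated elimination of high-titre children in 6.9.3. They apply the 2-fold rule to both subtypes, as 6.9.2 states. SAP Table 9 gives a different threshold for RSV-B (at or above the expected value), and the two need reconciling separately.

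**Room for handling terms in the Cox models.** Four storage and four tube categories plus one duration make 3 + 3 + 1 = 7 terms, or 70 events under the SAP's rule of 10 events per covariate. As an assumed proxy for severe LRTI, take the 0-5 month hospitalisation rates in Protocol Table 12 (16.9-44.1 per 1000 child-years). With 1920 children that gives 1920 × 0.25 × rate = 8-21 events at 0-2 months and 1920 × 0.5 × rate = 16-42 at 0-5 months. Even 2400 children give at most 2400 × 0.5 × 0.0441 = 53.

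**The case against.** The best defence is that nothing planned was removed. Protocol 6.5.5 says the data allow adjustment; it does not promise it. The co-primary analyses use no cord titre, and Protocol 9.7.2 and 9.7.3 name no handling term in the antibody models. A reader might infer that the SAP abandoned a specified model. The documents do not support that. What stands is narrower: the stated purpose is not carried through anywhere, and section 9 is silent. The reference to primary analyses is not empty either, because Protocol 9.7.2 and 9.7.3 use the same term for the main analyses of prevalence and decay.

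The models are also not closed. In 6.9.1, "depending on the data other models could be explored or the model could be simplified"; in 6.9.3, "Additional models such as models including a t^2 term or some covariates could be explored". These clauses are optional and name no handling variable, so they prespecify nothing. Country may stand in for site handling in the Cox models, but it enters only at a univariate p below 0.1 and cannot capture variation within a country. The decay and infection steps have no country term.

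Two further objections stand in full. No document shows a handling loss, and whether one exists is the tertiary question itself. Forcing about seven terms into the severe-LRTI models would also break the SAP's own events rule. It would not repair children already placed in the wrong titre quartile or serostatus group.

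**Conclusion.** The omission is confirmed, and its consequence is conditional. If handling lowers titre unevenly between samples, the log hazard ratio per log titre is attenuated by about 1-6% for a 1.2- to 1.4-fold loss in half the samples and 10-20% for a 2-fold loss. The decay rate is flattened, and more uninfected children are called infected at months 2, 4, 6 and 12. All sizes rest on assumed losses and SDs.

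Two stronger readings are tempting. One is that handling losses do distort these results; the documents give no evidence of a loss. The other is that false-infected shares of 23%, 30% or 50% would carry into prevalence. Those apply only to affected children with the curve held fixed at SD 1 log2. For the whole group the figures are about 17%, 18% and 22% against 15.9% with no loss, and the 1050 children at months 18 and 24 do not enter. A loss common to every sample is partly absorbed by the fitted curve, so uneven loss matters most for the infection rule.

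The point touches secondary and tertiary objectives and is a cheap improvement.

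**What to change.** 1. Correct the derivations first. SAP 11.2.3.4 should start at serum transfer, not birth. SAP 11.2.3.5 should state cord blood collection as its start time.
2. In 6.11.1, regress log cord titre on storage condition, tube type and collection-to-freezing time, with country in the model.
3. As a prespecified sensitivity analysis, repeat the quartile and continuous Cox models (6.9.1), the decay model (6.9.3) and the months 2-12 infection classification (6.9.2) with the handling-corrected cord titre. Repeat them again after excluding samples handled outside the recommended procedure. That procedure must be defined in the SAP or by reference to the study procedures manual, because neither document defines it.
4. Do not force handling terms into the Cox models. Correcting the titre beforehand uses none of their degrees of freedom.
5. State in section 9 that the main models are unadjusted for handling.

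The cost is SAP wording and some extra analysis on data already in the eCRF. If handling varies mainly by site, the correction may remove real titre differences between sites, which is why it should remain a sensitivity analysis.
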